3.3 DESCRIPTION OF THE STUDY DESIGN

This is a Phase I/IIa Multicenter, Double-Masked, Randomized, Vehicle-Controlled, Dose-ranging study designed to evaluate the safety and preliminary efficacy of TRS01 eye drops at three dose levels compared to vehicle in subjects with post-surgical inflammation.

Approximately 60 subjects with ocular inflammation following cataract surgery will be randomized at approximately five centers, in the USA and in France.

Subjects who provide informed consent and meet all study randomization criteria will be enrolled in the study and randomized in a 1:1:1:1 ratio to receive TRS01-█%, TRS01-█, TRS01-█% or vehicle eye drops four times daily.

The eye that underwent cataract surgery is defined as the study eye. TRS01 should not be administered in the fellow eye.

Treatment assignments will be masked to Tarsius, study subjects, Investigators, and site staff. In order to prevent unmasking, all study medications during the Treatment Period will be supplied in identical packages.

The study design includes 14-days of a double-masked treatment period, with the endpoint assessment conducted on Day 15 (FIGURE 1 summarizes the study phases, anticipated visits and number of subjects at each phase and Appendix 1 summarizes the schedule of assessments from Screening through Day 15).

Randomization is employed as an unbiased method of assigning subjects to four groups in equal allocation.

Male and female subjects aged 18 or older and 1-day post cataract surgery with anterior chamber cells \geq grade 2 in the study eye, are eligible to be randomized to participate in the treatment phase of the study.

[figure not shown]
Double-masked eye drops will be administered four times daily from Day 1 through Day 14 by the study participant (or care provider) to the study eye. The safety endpoint is on Day 15. Exploratory efficacy measurements will be collected.

Visits (including the surgery day):

1. Visit 1/Days -30 to -1 – Screening: Initial screening for eligibility – 1-30 days before the surgery.
2. Visit 2/Day 0 – Surgery: Eligible subjects will undergo routine cataract surgery according to investigator's standard procedures. No steroid or NSAID will be given before, during or after the surgery. Acetaminophen on the day of surgery is allowed.

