3. Visit 3/Day 1 – Randomization: Subjects who meet the post-surgery qualification criteria of \geq grade 2 anterior chamber cells in the study eye will be randomized and will initiate dosing with IP. The subject's first dose will occur after randomization under the observation of an Unmasked staff member.
 - 3.1. 40 minutes \pm 10 minutes post first dose, AEs, if any, will be recorded. Changes that are expected due to uncomplicated cataract surgery (such as discomfort, scratchy feeling, significant brightness, changes in the perception of the operated eye, corneal edema) will be collected, but will not be classified as AEs. Subjects will be given one bottle of IP and instructed to dose three more times that day and to begin dosing four times a day on the following day and onward.

4. Visit 4/Day 3: Evaluation
5. Visit 5/ Day 8: Evaluation and replacement of IP.
6. Visit 6/ Day 15: Evaluation, collection of IP and study completion.

FIGURE 1: STUDY VISITS

Please note that both eyes cannot be part of the study – there should be a treated eye (study eye) and an untreated eye (non-study eye). The non-study eye should not undergo any surgical procedure during the trial.

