3.3.3 Method to minimize bias

In order to prevent unmasking during the study, the three doses of TRS01 and the vehicle will be supplied in identical packages.

Treatment assignments during the treatment period will be masked to all Tarsius staff, subjects and investigators, except delegated unmasked site personnel. The designated unmasked site personnel should collect all AEs related to IP and will handle all IP related responsibilities but will not perform any study related assessments.

The first dose will be administered under the supervision of an unmasked staff member and will serve as confirmation that the subject was adequately trained on drop administration at the screening visit. In the event that it becomes necessary to unmask a specific subject's treatment assignment, the Principal Investigator will contact Tarsius Medical Officer or the back-up Medical Officer. Unmasking will be allowed for individual subjects after it is determined necessary by the Medical Officer and the Principal Investigator, thus leaving the masking of the remaining subjects intact

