4.3.1 Masking and Randomization Methodology

Eligible subjects will be randomized in a 1:1:1:1 ratio to receive TRS01 [REDACTED], TRS01 [REDACTED], TRS01 [REDACTED] % or vehicle dose on Day 1.

Randomization will occur after subjects meet all eligibility requirements at Screening and Day 1/Visit 3 (1-day post-surgery). Each subject will be assigned a unique subject number.

Each kit package (containing two IP bottles) will contain a kit number that can be later correlated to the subject number at the site.

Randomization for the US sites will be separate from the French site.

The randomization codes and all data sets will be stored in a secure area accessible only to delegated study personnel and only released on completion of the study and after the study database has been locked.

In this study all parties are to be masked to the allocated treatment; investigators, study staff and subjects. At the site, there will be designated unmasked study staff that will train the subject on all study procedures related to IP administration.

In emergency situations for reasons of subject safety (e.g. serious unexpected /unlisted drug related event; medical emergency; potentially life-threatening drug interaction) the masking code may need to be broken. In those cases, whenever possible, a request for unmasking should be discussed with the sponsor (or designee) prior to unmasking. Detailed instruction on the method for breaking the mask will be provided during site training and noted in the Investigator study file.

Following the first IP administration, if the subject perceives any AE that may be attributed to the IP, these should be reported to the unmasked site personnel.

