5.1.3 Visit 3: Day 1 (1-day post-surgery)

This visit should be scheduled to occur in the morning, if possible, to allow for QID dosing on Day 1 for randomized subjects. Perform the following assessments. Ocular assessments are to be performed on both eyes, unless otherwise noted:

- Subject-Rated Ocular Pain Assessment – prior to any other assessments
- Assessment of adverse events following subject rated ocular pain assessment. Changes that are expected due to uncomplicated cataract surgery will not be classified as AEs but will be recorded.
- Concomitant medication update
- Snellen Distance VA by Pinhole Method
- Slit-lamp biomicroscopy
- Intraocular pressure by Goldmann Applanation Tonometry
- Randomization: subjects that meet eligibility criteria ([section 1](#)) should be randomized to one of the treatment groups through the Interactive Web Response System (IWRS).
- [REDACTED]
- Dispensation of IP and Dosing Diary: the subject will receive one bottle from the study kit and will be instructed to self-administer the first drop prior to leaving the clinic, under the supervision of the unmasked personnel. The subject will be instructed to record this first dose and all subsequent doses in the dosing diary.
- 40 minutes \pm 10 minutes post IP administration the subject will be assessed for AEs in both eyes. If any AEs are reported at visit 3 that may be attributed to the IP, these should be handled by the unmasked personnel.
- The subject will be instructed to take the bottle home and administer the IP three more times that day. Following the day of this visit the subject will be instructed to begin using the drops four times a day and to continue for the duration of the study.

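### Adverse events are routed by presumed relation to study drug to staff exempt from masking, and nobody is named to separate AEs from expected surgical changes at the 40-minute check

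*Combined protocol and SAP*

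**What the plan says.** Three places in the protocol route AEs by presumed relation to the investigational product (IP).

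- Section 3.3.3, with no visit limit: "The designated unmasked site personnel should collect all AEs related to IP and will handle all IP related responsibilities". The same sentence continues that these staff "will handle all IP related responsibilities but will not perform any study related assessments". The sentence before it exempts them from masking.
- Section 4.3.1, for the period after the first administration: "if the subject perceives any AE that may be attributed to the IP, these should be reported to the unmasked site personnel".
- Section 5.1.3, for Day 1 only: "If any AEs are reported at visit 3 that may be attributed to the IP, these should be handled by the unmasked personnel".

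Sections 7.2.1, 7.3 and 7.4 give the rating of relation to IP to the Investigator or Principal Investigator, and 7.3 has the Investigator review each event. Investigators are masked.

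On who is masked, Section 3.3 states: "Treatment assignments will be masked to Tarsius, study subjects, Investigators, and site staff". Its Visit 3 paragraph then places the first dose "under the observation of an Unmasked staff member". Section 4.3.1 states: "In this study all parties are to be masked to the allocated treatment; investigators, study staff and subjects". Its next sentence names designated unmasked staff at the site.

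**The concern.** An event cannot be routed by its relation to IP until someone has formed a view on that relation. The rule therefore asks for a provisional attribution at collection, while the formal one comes from a masked Investigator. Nothing says how a report gets from the first person to the second, or in what form.

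The 40-minute check is where this matters most. It is the first look after exposure, and drop reactions can resemble the effects of surgery. Section 3.3 counts discomfort and a scratchy feeling among expected changes, and the pain scale in 8.1.3 treats brief mild stinging as typical after cataract surgery. Someone has to decide which of these complaints are AEs, and the protocol does not say who.

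Safety is the primary objective. Section 3.1 puts treatment-related AEs in the primary safety parameter, and 9.1.2 tabulates them by group. If the person who sorts complaints knew or guessed the arm, the sorting could differ between arms.

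**Working it through.** No figure in the protocol bears on this point, so the check compares the text.

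**1. Who receives the report.** Unmasked site staff, under 3.3.3 (any visit), 4.3.1 (after the first dose) and 5.1.3 (Visit 3). The three scopes differ. The trigger differs too: relation to IP in 3.3.3, the subject's own perception in 4.3.1, and an attribution by an unstated person in 5.1.3.

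**2. Who rates relatedness.** The Investigator (7.2.1, 7.3) or Principal Investigator (7.4), masked under 3.3, 3.3.3 and 4.3.1. No section describes the transfer from step 1 to step 2.

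**3. Who separates AEs from expected changes at 40 minutes.** Section 3.3 says that AEs are recorded and that expected changes are collected without being classified as AEs. Section 5.1.3 says that the subject is assessed. Appendix 1 marks AE assessment in the post-dose column, with a footnote on expected changes. None of the three names a role.

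**4. Whether 3.3.3 settles step 3 indirectly.** It bars unmasked staff from study-related assessments.
- If AE assessment counts as one, these staff may not do the sorting, but nobody else is named for the check.
- If collecting is not assessing, there is no contradiction, but the person who assesses is still unstated.

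Either way the classifier is undefined.

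**5. The same judgement is made twice.** In 3.3, 5.1.3 and Appendix 1, an expected effect of surgery keeps a complaint out of the AE set. In 7.3, an event easily explained by uncomplicated surgery is an AE that the Investigator rates Unrelated. The first judgement has no owner. The second belongs to the Investigator.

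**6. What reaches the table.** Take a complaint that passes through a collector who is not the Investigator.
- Both would call it surgical: it is outside the treatment-related table either way.
- Both would call it a drug-related AE: it is in the table.
- The collector calls it a possible drug reaction and the Investigator disagrees: the Investigator's review under 7.3 corrects it.
- The collector calls it an expected change, and the Investigator would have rated it probable or definite: it is recorded (3.3) and listed (9.1), but it is not in the treatment-related table (9.1.2).

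Only the last case does damage. For it to differ between arms, the collector must also sort differently by arm. The documents give no AE rates, no disagreement rates and nothing on sorting by arm, so no size can be computed.

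**The case against.** The strongest reply is that the protocol never gives unmasked staff a classification decision. The Investigator reviews each event, so the treatment-related table rests on the Investigator's rating and not on who took the report. The only person named as attributing a complaint is the subject (4.3.1), who is masked. AEs are captured by verbatim term (Synopsis), and 7.4 requires neutral opening questions. Sections 5.1.4 to 5.1.6 name unmasked personnel for diary and IP tasks but not for AE assessment. Keeping complaints away from the investigator who grades cells and flare is also a reasonable aim. Much of the masking conflict is a general rule followed by its exception.

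Most of this stands, and it rules out several stronger readings that a reader might infer.

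- **That unmasked staff decide relatedness.** No passage says so. An early attribution is implied by the routing rule, but it is not assigned to them.
- **That these staff know the arm.** This cannot be determined. Packages are identical (3.3.3), and the randomization codes are "only released on completion of the study and after the study database has been locked", although stored with access for delegated personnel. No text survives under 3.3.1 in the public copy, and that gap is not a fault of the plan.
- **That a Day 1 complaint classed as surgical is lost.** It is recorded and listed whether or not the subject mentions it again.
- **That the small arms measure the harm.** Sixty subjects in four arms is 60/4 = 15 per arm, so one subject is 1/15 = 6.7 percentage points. That holds for any event in any such arm and says nothing about this routing.

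The reply does not supply a named classifier at 40 minutes or a written handover. Investigator review of each event protects only complaints that reach the Investigator as events.

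**Conclusion.** The point holds as a gap in procedure, not as a demonstrated bias. The protocol sets an attribution-based collection rule for part of its primary safety data, routes those reports to staff exempt from masking, writes no handover to the masked rater, and leaves the AE decision at the 40-minute check without an owner. This is an avoidable possible route for differential classification of treatment-related AEs. Its size and direction are unknown.

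Bias between arms would require three things that the documents do not establish: that someone other than the masked Investigator does the sorting, that the two would disagree, and that the disagreement varies by arm. If the unmasked staff do not know the arm, bias through their knowledge falls away, but the unnamed classifier, the missing handover and the inconsistent masking text remain.

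It should be fixed because the remedy is cheap and the data are primary. Confidence is medium.

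**What to change.** Amend 3.3.3, 4.3.1 and 5.1.3 as follows.

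1. Any complaint reported to unmasked staff, including at the 40-minute check, is recorded verbatim without attribution and passed to the masked Investigator without allocation information.
2. Only the masked Investigator decides AE versus expected surgical change, severity and causality.
3. The role that performs the 40-minute check is named.
4. The masking statements in 3.3, 3.3.3 and 4.3.1 are reconciled into one that says which staff are unmasked and that they make no AE classification.

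The cost is amendment wording, site retraining and a revised delegation log. The downside is that the investigator who must score cells and flare at Visits 3 to 6 (8.1.1) may hear slightly more complaints that hint at treatment. The added exposure is small, because 7.3 and 7.4 already require Investigator review and a causality rating for each event.

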4 SELECTION OF STUDY POPULATION

4.1 SUBJECT INCLUSION CRITERIA

Pre-operatively, individuals of either gender or any race will be eligible for study participation if they are:

1. 18 years of age or older.
2. Able to provide informed consent, follow instructions and complete all required study visits for the duration of the study.
3. Scheduled for routine cataract surgery (phacoemulsification or extracapsular extraction) with posterior chamber intraocular lens (IOL) implantation, and not combined with any other surgery.
4. Have vision $\geq 20/200$ in the non-study eye.
5. Able to self-administer eye drops (tested during screening by self-administration of “artificial tears”), or have a care provider that can administer the drops.
6. Have no known sensitivity /allergy to the TRS01 or formulation excipients as detailed in **TABLE 2** and **TABLE 3**.
7. Using adequate birth control by men and women, if of reproductive potential and sexually active. Adequate birth control is defined as agreement to consistently practice an effective and accepted method of contraception throughout the duration of the study and for 2 weeks after the last dose of investigational product.
 - a. For females, adequate birth control methods will be defined as hormonal contraceptives, intrauterine device or double barrier contraception, i.e., condom + diaphragm, condom or diaphragm + spermicidal gel or foam.
 - b. For males, adequate birth control methods will be defined as double barrier contraception, i.e., condom + diaphragm, condom or diaphragm + spermicidal gel or foam.
 - c. For females, menopause is defined as one year without menses; if in question, a follicle-stimulating hormone of >40 IU/L must be documented. Hysterectomy, bilateral oophorectomy, or bilateral tubal ligation must be documented, as applicable.

4.2 SUBJECT EXCLUSION CRITERIA

In order for subject to be eligible at Visit 1 they may not:

1. Be scheduled to undergo cataract surgery in the non-study eye for 2 months prior to Visit 1 and during the study.
2. Require use of any topical ophthalmic medication (either eye) for 14 days prior to surgery and for the duration of the trial. Note: Use of PRN artificial tears up to twice a day is allowed and should not be dosed within 10 minutes of investigational product dosing.

3. Require topical ocular therapy (either eye) with antibiotics for 30 days prior to surgery except antibiotic eye drops used as part of the Investigator's routine pre-op, intra-op, and post-op routine care.
4. Require treatment with systemic NSAIDs, within 14 days prior to the surgery and for the duration of the trial. Occasional use (\leq 2 times per week) of NSAIDs or over the counter (OTC) painkillers to treat minor non ocular conditions is acceptable. Low-dose aspirin (81 mg) for cardiovascular prophylaxis is allowed. Acetaminophen is the preferred treatment for post-op pain on the day of surgery.
5. Require treatment with systemic or ocular immunosuppressants or immunomodulators including systemic steroids (oral, inhaled, injectable) for 30 days prior to surgery and for the duration of the trial. Require treatment with nasal, topical dermal steroids or immunosuppressants within 14 days prior to surgery and for the duration of the trial. Require treatment with alpha-1 antagonists within 30 days of surgery and for the duration of the trial.
6. Use any ocular, topical or systemic medication that could interfere with wound healing, the test agent, or the interpretation of study results, within 30 days prior to the day of surgery and for the duration of the trial.
7. Use of contact lenses in the study eye are prohibited for the duration of the study.
8. Have history of glaucoma surgery or any incisional ocular surgery in the study eye. History of uncomplicated refractive surgery 3 years prior to the cataract surgery is acceptable.
9. Have any significant ocular disease in the study eye in addition to the cataract that may confound the trial results per the Investigator's judgement.
10. Have proliferative diabetic retinopathy (PDR), not stable for at least one year in the study eye.
11. Be currently being treated for wet macular degeneration.
12. Have current or history of herpes keratitis in the study eye.
13. Be diagnosed with Fuchs Corneal Dystrophy (FCD).
14. Have current or history of prior ocular inflammation in the study eye not related to prior allowed surgical procedure.
15. In the opinion of the Investigator, have current clinically significant dry eye requiring therapy of greater than twice a day (BID) eye drops in the study eye. Use of PRN artificial tears up to twice a day is allowed and should not be dosed within 10 minutes of investigational product dosing.
16. Use any Cannabidiol products during the trial.
17. Have history of glaucoma or uncontrolled IOP >22 mmHg in the study eye on day of screening.

18. Have floppy iris syndrome noted for the contralateral eye prior to surgery in the study eye.
19. Have any clinically significant systemic disease or condition (e.g. hematological diseases) that, in the Investigator's opinion, may confound the trial results, pose a safety risk to the subject or preclude the subject from adhering to the protocol or completing the trial per protocol and installing eye drops.
20. Have a known history of alcohol and/or drug abuse.
21. Be an employee of the site that is directly involved in the management, administration, or support of this study or be an immediate family member of the same.
22. Have been exposed to an investigational drug or investigational medical device within 60 days prior to Visit 1.
23. Be pregnant or lactating.

4.3 RANDOMIZATION INCLUSION CRITERIA

To qualify for randomization at the Day 1 (Visit 3), a subject must:

1. Have undergone routine, uncomplicated cataract surgery (phacoemulsification or extracapsular extraction) with posterior chamber IOL implantation, not combined with any other surgery (including but not limited to use of iris retractors, capsular fixation ring or anterior capsule staining with dye). Specifically, have NOT had any cataract surgery complication such as a posterior capsular rupture, vitreous loss or significant iris damage.
2. Have an IOP of \leq 30 mmHg. Notes: Fluid release from the anterior chamber through the surgical incision is allowed (manual burping). The final IOP post release of fluid must be \leq 30 mmHg and will be recorded as the visit IOP value. Use of IOP lowering medications are allowed beginning on Day 0, with the exception of prostaglandins. IOP lowering eye drops should be dosed at least 30 minutes before investigational product dosing.
3. Have anterior chamber cells \geq grade 2.
4. Continue to meet inclusion/exclusion criteria with respect to current ocular and medical conditions and must not be taking prohibited medications (section 6.4).

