1 INTRODUCTION

Intraocular inflammation is a typical undesirable consequence of intraocular surgery such as cataract surgery. It is manifested principally as conjunctival injection, corneal edema, ciliary flush and aqueous cells and flare. Surgical trauma and phacoemulsification energy activate an inflammatory cascade that ultimately leads to formation of prostaglandins, which results in local vasodilation and increased vascular permeability.

Inflammation may resolve with no treatment in 15-28% of patients. However, inadequately treated inflammation after cataract surgery frequently causes pain, photophobia, increased risk for elevated intraocular pressure (IOP), corneal edema, corneal scarring and cystoid macular edema [Aptel et al., 2017]. Thus, managing and treating postoperative inflammation is an important goal following cataract surgery.

Other ocular inflammatory diseases include, for example, non-infectious uveitis, a potentially blinding condition that is the fifth leading cause of visual loss in the developed world (third leading cause of preventable blindness), has been estimated to account for 10% of all visual impairment in the western world and 10–15% of cases of total blindness [Nussenblatt, 1990; Merida et al., 2015]. Anterior uveitis accounts for approximately 80% of non-infectious uveitis cases in the United States [Thorne et al., 2016].

Uveitis is characterized by an inflammatory process that may be acute, recurrent, chronic or acute-on-chronic. Untreated, recurrent bouts of uveitis eventually lead to tissue destruction from direct inflammation or from complications such as cataract, glaucoma and macular edema.

Topical corticosteroids represent first line treatment for both non-infectious uveitis and postoperative inflammation. In the US, topical corticosteroids are routinely prescribed with four times daily (QID) dosing for at least 2 weeks following cataract surgery [Kim et al., 2019].

The side effects associated with steroid use, significantly limit prolonged treatment. The most common adverse effects of ocular steroids are cataract and elevated IOP which can lead to steroid related glaucoma.

Given the limitations of treatment, there is a need for an effective anti-inflammatory drug that does not have an IOP-elevating effect. Tarsius Pharma has developed a novel therapeutic approach for local prevention and treatment of ophthalmic inflammatory diseases. [REDACTED]

[REDACTED]

[REDACTED]

[REDACTED]

[REDACTED]

[REDACTED]

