6.4 MEDICATIONS NOT PERMITTED

Use of the following medication is not permitted during the study and **14** days prior to Visit 2 (Day of Surgery):

1. Any topical ophthalmic medications (either eye) other than study required medications. Note: Use of PRN artificial tears up to twice a day (BID) is allowed, and should not be dosed within 10 minutes of investigational product dosing.
2. Prostaglandins. Use of IOP lowering medications, other than prostaglandins, are allowed beginning on Day 0 and during the study, as needed. IOP lowering eye drops should be dosed at least 30 minutes before investigational product dosing.
3. Systemic NSAIDs. Occasional use (≤ 2 times per week) of Systemic NSAIDs or OTC painkillers to treat minor non-ocular conditions is acceptable. Low- dose aspirin for cardiovascular prophylaxis is allowed. Acetaminophen may be administered pre and post-operatively as needed for pain on the day of surgery.
4. Treatment with nasal, topical dermal steroids or immunosuppressants.

Use of the following medication is not permitted during the study and 30 days prior to Visit 2 (Day of Surgery):

1. Use of topical ocular therapy (both eyes) with antibiotics. Note: Antibiotic eye drops that are routinely administrated prior/during and post cataract surgery are allowed.
2. Use of systemic or ocular immunosuppressants or immunomodulators including steroids (oral, inhaled, injectable, nasal, topical dermal).
3. Use of systemic alpha-1 antagonists.
4. Any ocular, topical or systemic medication that could interfere with wound healing, the test agent, or the interpretation of study results.
5. Other investigational drugs or devices

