7.2 SAFETY VARIABLES

Safety measures include AEs/SAEs and clinical assessments from the slit-lamp biomicroscopy findings, IOP, and dilated ophthalmoscopy findings.

AEs and ocular safety measures to be collected in this study are listed in [Table 4](#).

TABLE 4: OCULAR SAFETY MEASURES

Safety Measure	Note
Slit-lamp biomicroscopy: Lid hyperemia, lid edema, conjunctival hyperemia, chemosis, corneal edema, conjunctival discharge/exudate	The status of each of these biomicroscopy parameters will be rated as 0 = None, 1 = Mild, 2 = Moderate, or 3 = Severe. For each abnormal record, the clinical significance (Clinically Significant or Not Clinically Significant) will also be determined. Slit-lamp biomicroscopy will be performed at all study visits, except Visit 2 (Surgery).
Intraocular pressure	The IOP measurements will be performed by Goldmann applanation tonometry. IOP pressure recorded in mmHg (e.g., 18mmHg). IOP measurements will be performed at all study visits, except Visit 2 (Surgery).
Dilated Ophthalmoscopy: IOL (post-surgery), vitreous haze, retina vessels, macula, optic nerve, cup/disc ratio.	The status of IOL position, macula and optic nerve will be determined as Normal or Abnormal. The cup/disc ratio will be recorded with two decimal points (e.g., 0.80). Dilated ophthalmoscopy will be performed at Visit 1 (Screening) and at Visit 6 (Day 15).

Intraocular Pressure (IOP) – IOP will be measured using Goldmann Applanation Tonometry with a single measurement.

These ocular safety measures will be summarized using descriptive statistics. For continuous ocular safety measures, changes from Baseline (Day 1 / Visit 3) variables will also be summarized descriptively.

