9.1.2 Analysis of Safety

Analysis of safety data will be presented for all subjects. AEs will be coded using Medical Dictionary for Regulatory Activities (MedDRA, most current version) and categorized by system organ class using preferred terms. Treatment emergent AEs will be listed by study group. Treatment related AEs will be tabulated by study group and will be reported by incidence (both number of events and number of subjects) with respect to their intensity and relationship to the IP. Ophthalmoscopy findings will be summarized descriptively. IOP measurements, VA, and slit lamp biomicroscopy will be summarized as safety outcomes.

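### IOP change is measured from a Day 1 value that may follow fluid release or IOP-lowering drugs, and drops started after randomization can mask a difference between arms

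*Combined protocol and SAP*

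**What the plan says.** Section 4.3, item 2, permits manual release of fluid through the incision at the Day 1 visit. The final reading after release must be no more than "30 mmHg and will be recorded as the visit IOP value". The same item adds: "Use of IOP lowering medications are allowed beginning on Day 0, with the exception of prostaglandins". Section 6.4 extends this past randomization: "Use of IOP lowering medications, other than prostaglandins, are allowed beginning on Day 0 and during the study, as needed".

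On measurement, Section 7.2 states that "IOP will be measured using Goldmann Applanation Tonometry with a single measurement". On analysis it states: "For continuous ocular safety measures, changes from Baseline (Day 1 / Visit 3) variables will also be summarized descriptively". Section 9.1.2 adds only that "IOP measurements, VA, and slit lamp biomicroscopy will be summarized as safety outcomes". Section 9.1 has all data listed by treatment, subject and visit.

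IOP is also measured at screening by the same method (Section 5.1.1). Section 4.2, item 17, excludes a history of glaucoma or uncontrolled IOP above 22 mmHg in the study eye at screening. Section 6.1 collects the name, indication, dose and dates of every concomitant drug.

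The visible text does not say whether a pre-release reading is kept, how readings taken on IOP-lowering drugs are handled, or what counts as an IOP rise.

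**The concern.** Safety is the primary objective, IOP is a listed safety endpoint (Section 3.1), and the Introduction justifies the product by saying that "there is a need for an effective anti-inflammatory drug that does not have an IOP-elevating effect". Readers will look closely at the IOP tables.

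The Day 1 value can mean different things in different subjects. In a burped eye it is one mechanically lowered reading. In an unburped eye it may be a post-surgical pressure of up to 30 mmHg. In either, it may already be on an IOP-lowering drug. Follow-up readings may be on such drugs as well. A change from Day 1 then mixes fluid release, recovery from surgery, IOP-lowering medication and any effect of TRS01.

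The two sources differ in kind. Release happens before randomization and cannot depend on the assigned arm. Drops started after randomization can: if TRS01 raised IOP, more TRS01 subjects would need them. Masking the investigators does not prevent this, because the need itself would differ.

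**Working it through.** **Inputs.** About 60 subjects randomized 1:1:1:1 (Section 3.3), so 60/4 = 15 per arm. One IOP reading per visit (Section 7.2). Day 1 limit 30 mmHg (Section 4.3). The documents give no IOP standard deviation, no share of eyes burped, no share on drops and no size of drop effect, and the sample size text in Section 9.2 is redacted. There is no planned figure to reproduce, and all IOP values and shares below are assumptions.

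**Step 1: single eyes.** Change = follow-up reading minus reference reading (mmHg).

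| Eye | Screening | Day 1 recorded | Follow-up | Change from Day 1 | Change from screening |
|---|---|---|---|---|---|
| A: burped from 34 to 8 | 15 | 8 | 16 | 16 − 8 = +8 | 16 − 15 = +1 |
| B: burped from 34 to 15 | 15 | 15 | 16 | 16 − 15 = +1 | 16 − 15 = +1 |
| C: not burped | 15 | 28 | 22 | 22 − 28 = −6 | 22 − 15 = +7 |
| D: not burped, no drops | 16 | 28 | 30 | 30 − 28 = +2 | 30 − 16 = +14 |
| E: as D, drops lower IOP by 6 | 16 | 28 | 24 | 24 − 28 = −4 | 24 − 16 = +8 |

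A and B differ only in where release left the eye. Against screening, what matters is the gap between the recorded Day 1 value and the screening value (15 − 8 = 7 in A, 0 in B). The size of the fall (26 in A, 19 in B) does not measure it. C to E show a high Day 1 value concealing a level well above screening.

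**Step 2: imbalance in burping between two arms.** Let X and Y be the numbers of burped eyes in two arms, each Binomial(15, p). Both are fixed before randomization, so their expected difference is zero. The chance that |X − Y| is 3 or more is:

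- p = 10%: 0.12
- p = 20%: 0.25
- p = 30%: 0.32

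This is noise, and at 15 per arm it is not negligible.

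**Step 3: drops started after randomization.** At a given visit,

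observed difference = true difference − (share on drops, active − share on drops, vehicle) × drop effect.

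Take a true active-minus-vehicle difference of 3 mmHg:

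- 20% versus 20%, any effect: 3 − 0 = 3.0
- 30% versus 10%, 4 mmHg: 3 − 0.20 × 4 = 2.2
- 40% versus 10%, 6 mmHg: 3 − 0.30 × 6 = 1.2
- 50% versus 10%, 8 mmHg: 3 − 0.40 × 8 = −0.2

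The Day 1 mean has the same expectation in all arms, so the attenuation applies equally to mean change and to mean observed IOP.

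**The case against.** The strongest reply is that the plan does not rest on change from Day 1 alone. Section 7.2 summarizes the measures themselves and then also their changes; Section 9.1 lists everything. Observed IOP on Days 3, 8 and 15 against vehicle does not depend on the Day 1 value. A rise found at a visit and then treated would normally leave its high reading in the data, unscheduled visits also call for IOP (Section 5.1.7), and drug dates and AEs are collected. Day 1 is the natural pre-dose baseline, and screening IOP predates surgery, so change from screening carries the effect of surgery. All of this stands.

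It does not dispose of the point. Observed means taken on drops are attenuated just as changes are (Step 3). AE reporting is not a count against a set threshold, and Section 3.1 keeps expected surgical changes out of the AEs. Listings hold the facts, but no visible table brings IOP and medication together.

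A reader might infer more than the documents support:

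- That the planned measures cannot answer the IOP safety question. Observed values, listings, AEs and medication dates are all planned.
- That burping favours one arm. It precedes randomization.
- That a treated rise always appears as no change. That depends on when the reading is taken and how large the drop effect is.
- That no screening IOP can exceed 22 mmHg. The exclusion refers to uncontrolled IOP above that figure.
- That a pre-release value always exists. No text makes release conditional on a reading, and Section 7.2 specifies one measurement.

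Section 9.1 defers to a Statistical Analysis Plan whose text is not in hand, nor is the eCRF, and the rescue criteria in Section 7.2.2 are redacted. Any of these may already cover part of the gap.

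**Conclusion.** The point holds in a limited form, with medium confidence. Under the visible plan, changes in IOP from Day 1 are hard to interpret for single eyes and within arms. Burping adds chance imbalance between arms of about 15 but no systematic bias.

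The more important part is medication after randomization. If its use depends on treatment, it shrinks a true difference in both mean change and observed means: from 3 mmHg to 1.2 mmHg in the central assumed case, and to between 2.2 and −0.2 mmHg across the range shown. With equal use in the arms the difference is not attenuated. These figures rest entirely on assumed shares and drop effects.

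Most of the data for a repair will be collected. The exception is the pre-release reading, whose recording is not specified and which no later analysis can recover.

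**What to change.** 1. In Section 4.3 and the eCRF, record any pre-release Day 1 IOP separately from the post-release value, and flag burped eyes.
2. In Sections 7.2 and 9.1.2, report study-eye IOP change from screening (Visit 1) beside change from Day 1, with a note that the former includes the effect of surgery.
3. In Section 9.1.2, tabulate by arm the number of subjects who, after the first dose, have IOP above prespecified reporting cut-offs or start or increase IOP-lowering medication. The protocol's eligibility figures of 22 and 30 mmHg could serve as cut-offs; they would be reporting conventions only. Counting medication together with raised readings keeps a treated rise visible, and the vehicle arm shows how much is due to surgery.

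The cost is an eCRF field with its flag and one or two tables. Permitted treatment is unchanged. If the SAP or eCRF already contains any of these items, a cross-reference is enough.
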